#### 3.5.1. Adverse Events

An adverse event is considered treatment emergent (TEAE) relative to a given treatment if:

- the event occurs during the on-treatment period (regardless if it was seen prior to the start of treatment)

CCI  
[Redacted text block containing multiple lines of blacked-out content]

## **Adverse Events of Special Interest (AEoSI)**

The current full list of AEoSI and MedDRA high level terms (HLT), standardized MedDRA queries (SMQ), and/or preferred terms (PTs) included in each event are listed in a separate AEoSI cluster document. These events will be defined based on a list of MedDRA Preferred Terms specified in the Safety Review Plan for glasdegib. A final list will be provided to programming prior to database release.

### **3.5.2. Laboratory Data**

Hematology, chemistry, lipid and coagulation tests results will be programmatically graded according to the NCI CTCAE version 4.03 for relevant parameters. Parameters which cannot be graded will be summarized relative to the normal range (ie, normal range high or normal range low). Additional details are provided in [Section 6.6.3](#).

## **4. ANALYSIS SETS**

Data for all patients will be assessed to determine if patients meet the criteria for inclusion in each analysis population prior to unblinding and releasing the database and classifications will be documented per standard operating procedures. The intensive and non-intensive chemotherapy patients are always analyzed separately.

### **4.1. Full Analysis Set**

The Full Analysis (FA) set will include all randomized subjects. Subjects will be classified according to the treatment assigned at randomization.

Randomized but not treated patients will be reported under their randomized treatment group for the full analysis set. The FA set will be the primary population for evaluating all efficacy and PRO endpoints CCI [REDACTED] and patient characteristics.

### **4.2. Per Protocol Analysis Set**

Not applicable.

### **4.3. Safety Analysis Set**

The Safety Analysis (SA) set will include all subjects who receive at least one dose of study drug.

A randomized but not treated patient will be excluded from this safety analysis set. Subjects will be classified according to the treatment assigned at randomization unless the incorrect treatment(s) was/were received throughout the dosing period in which case subjects will be classified according to the first study treatment received. The SA set will be the primary population for evaluating treatment administration/compliance and safety, CCI [REDACTED]. Efficacy endpoints may be assessed in this population as well.

#### 4.4. Other Analysis Sets

##### 4.4.1. Pharmacokinetics Analysis Set

The PK concentration analysis set is defined as all subjects who are treated and who have at least 1 value of analyte concentration of glasdegib available. The PK parameter analysis set is defined as all subjects who are treated and who have at least 1 of the PK parameters of interest. Subjects will be classified according to the treatment assigned at randomization unless the incorrect treatment(s) was/were received throughout the dosing period in which case subjects will be classified according to the first study treatment received.

CCI [REDACTED]

[REDACTED]

[REDACTED]

[REDACTED]

[REDACTED]

[REDACTED]

##### 4.4.3. China Sub-Population Analysis Sets

For each efficacy, safety, CCI [REDACTED] and pharmacokinetics analysis set defined above, the corresponding China subset analysis set is the subset of patients consisting of patients enrolled in mainland China.

## 5. GENERAL METHODOLOGY AND CONVENTIONS

### 5.1. Hypotheses and Decision Rules

#### 5.1.1. Hypotheses and Sample Size Section

The hypotheses and sample size calculation were done independently and separately for the patients in the two studies.

#### Intensive Chemotherapy Study:

The primary objective of the study is to demonstrate that glasdegib in combination with 7+3 (Arm A) is superior to placebo in combination with 7+3 (Arm B) in prolonging OS.

The study is designed to test  $H_0: HR \geq 1$  vs.  $H_A: HR < 1$ , where HR is the hazard ratio (Arm A/Arm B) of OS.

A total of 400 subjects eligible to receive intensive chemotherapy per investigator assessment will be enrolled into the study. A total of 267 death events to be observed in the study would provide 90% power to detect an improvement in overall survival translated in mOS from 21 months to 31.5 months assuming a composite mOS for the population as follows: young AML (aged  $\leq 60$  years) with a mOS of 23.7 months and elderly AML (aged  $> 60$  years) with a mOS of 15 months assuming a 70% young and 30% elderly AML split and with an  $HR=0.67$  using a 1-sided log-rank test at a significance level of 0.025 and a 3-look group-sequential design.

The sample size of 400 subjects is determined based on the assumption of a HR of 0.67 under the alternative hypothesis (under an exponential model, translating in median OS of 31.5 months in the treatment arm and 21 months in the control arm) expecting approximately one third of all enrolled subjects to be censored. It is assumed a ramping enrollment of 10 months to reach a maximum enrollment of 18 patients/month. An accrual duration of 28 months to randomize 400 patients and an overall trial duration of 58 months is expected.

For the China subset, no formal statistical testing will be conducted.

#### **Non-Intensive Chemotherapy Study:**

The primary objective of the study is to demonstrate that glasdegib in combination with azacitidine (Arm A) is superior to placebo in combination with azacitidine (Arm B) in prolonging OS.

The study is designed to test  $H_0: HR \geq 1$  vs.  $H_A: HR < 1$ , where HR is the hazard ratio (Arm A/Arm B) of OS.

A total of 320 subjects who are not candidates to receive Intensive Chemotherapy will be enrolled into the study. A total of 220 death events to be observed in the study would provide 90% power to detect an improvement in overall survival translated in mOS from 10.4 months to 16.2 months with an  $HR=0.64$  using a 1-sided log-rank test at a significance level of 0.025 and a 2-look group-sequential design. One interim efficacy and futility analysis of OS would be planned after 60% death events occur in the non-intensive chemotherapy population or upon completion of enrollment of these subjects, whichever is later.

The sample size of 320 subjects is determined based on the assumption of a HR of 0.64 under the alternative hypothesis (under an exponential model, translating in median OS of 16.2 months in the treatment arm and 10.4 months in the control arm) expecting approximately 31% of all enrolled subjects to be censored. It is assumed a ramping enrollment of 10 months to reach a maximum enrollment of 18 patients/month. An accrual duration of 23 months to randomize 320 patients and an overall trial duration of 37 months is expected.

For the China subset, no formal statistical testing will be conducted.

### 5.1.2. Decision Rules

The interim analyses will be performed based on the FA set for the intensive and non-intensive chemotherapy populations separately and independently of each other as described in the following. The key secondary Fatigue endpoint will be analyzed using a hierarchical testing procedure, provided the primary OS endpoint is statistically significant favoring the experimental arm within each patient population (intensive and/or non-intensive).

An interim analysis will not be performed for the China subset. Full analysis following early stopping at an interim analysis or following final analysis will be carried out for the China subset based on the specifications in other sections.

Non-binding for the futility implies that the futility boundary will be constructed in such a way that it can be overruled if desired by the external data monitoring committee (E-DMC) without inflating the type-1 error rate and without decreasing the power.

#### Intensive Chemotherapy Study:

Two interim analyses are planned. One efficacy and futility interim analysis is planned when 50% of death events have occurred in the intensive chemotherapy population. However, no efficacy stopping will be made even if the interim analysis result crosses the efficacy boundary. A second interim analysis of efficacy and futility is planned when 70% of death events have occurred or upon completion of enrollment of the intensive chemotherapy population, whichever is later. An O'Brien-Fleming boundary with Lan-DeMets spending function will be used for efficacy and a Rho(3)  $\beta$ -spending function will be used for the non-binding futility boundary. If exactly 50% of the events is accrued at the first interim analysis, the futility boundary will be crossed when 1-sided  $p > 0.461$ . If exactly 70% of the events is accrued at the second interim analysis, the futility boundary will be crossed when 1-sided  $p > 0.186$  and the efficacy boundary will be crossed when 1-sided  $p < 0.007$ . If the actual number of events at the interim analyses is different, the corresponding spending function will be used to calculate the actual stopping boundaries. A 1-sided  $p < 0.023$  at the final analysis suggests the null hypothesis is to be rejected.

**Table 2. Planned Stopping Boundaries for Overall Survival at Interim Analyses and Final Analysis for the Intensive Chemotherapy Study**

Analysis	Number of Events (%)	Cumulative Alpha Spent	Cumulative Beta Spent	Futility Boundary p-value	Efficacy Boundary p-value
First IA	134 (50%)	0.002	0.013	0.461	*
Second IA	187 (70%)	0.007	0.034	0.186	0.007
FA	267 (100%)	0.025	0.100	0.023	0.023

Abbreviations: IA=interim analysis; FA=final analysis

The cumulative alpha spent, cumulative beta spent, and boundaries were calculated using software EAST (version 6.4).

\* No stopping for efficacy regardless whether the efficacy boundary is crossed or not.

## Non-intensive Chemotherapy Study:

One interim analysis is planned. An interim analysis of efficacy and futility is planned when 60% of death events have occurred or upon completion of enrollment of the non-intensive chemotherapy population, whichever is later. An O'Brien-Fleming boundary with Lan-DeMets spending function will be used for efficacy and a Rho(3)  $\beta$ -spending function will be used for the non-binding futility boundary. If exactly 60% of the events is accrued at the interim analysis, the futility boundary will be crossed when 1-sided  $p > 0.302$  and the efficacy boundary will be crossed when 1-sided  $p < 0.004$ . If the actual number of events at the interim analyses is different, the corresponding spending function will be used to calculate the actual stopping boundaries. A 1-sided  $p < 0.024$  at the final analysis suggests the null hypothesis is to be rejected.

**Table 3. Planned Stopping Boundaries for Overall Survival at Interim Analyses and Final Analysis for the Non-Intensive Chemotherapy Study**

Analysis	Number of Events (%)	Cumulative Alpha Spent	Cumulative Beta Spent	Futility Boundary p-value	Efficacy Boundary p-value
IA	132 (60%)	0.004	0.021	0.302	0.004
FA	220 (100%)	0.025	0.100	0.024	0.024

Abbreviations: IA=interim analysis; FA=final analysis

The cumulative alpha spent, cumulative beta spent, and boundaries were calculated using software EAST (version 6.4).

## 5.2. General Methods

Unless otherwise specified, baseline data will be summarized by treatment arm and for both treatment arms combined. Disposition, efficacy, exposure (including concomitant therapies), and safety data will be summarized by treatment arm only. The intensive and non-intensive chemotherapy patients will be analyzed separately.

### 5.2.1. Pooling of Data by Center

Each study is expected to enrol in more than 20 countries and more than 100 sites. In order to provide overall estimates of treatment effects, data will be pooled across centers. The 'center' factor will not be considered in statistical models or for subset analyses due to the high number of participating centers in contrast to the anticipated small number of patients randomized/treated at each center.

No pooling across centers will be done for the China subset analysis.

### 5.2.2. Definition of Study Day

Start day of study treatment is the day of the first dose of study treatment.

The study day for assessments occurring on or after the first dose of study treatment (eg, adverse event onset, laboratory date) will be calculated as:

Study day = Date of the assessment/event - start date of study treatment + 1.

The study day for assessments occurring prior to the first dose of study treatment (eg, baseline characteristics, medical history) will be negative and calculated as:

Study day = Date of the assessment/event – start date of study treatment.

The study day will be displayed in all relevant data listings.

### **5.2.3. Definition of Cycle and Cycle Day**

#### **Non-intensive Chemotherapy Study**

Cycle start and end dates are derived per patient and not per study treatment.

- For Cycle X, the actual cycle start date for each subject is the earliest start date of dosing (dose>0 at that visit ) in Cycle X visit CRF exposure page.
- For all but the last cycle.
  - actual cycle end date is calculated as the start date of the next cycle minus one day.
  - actual cycle duration is calculated from Day 1 of a cycle to the day prior to Day 1 of the next cycle, as follows:

$$\text{Actual Cycle Duration} = \text{cycle end date} - \text{cycle start date} + 1.$$

- For the last cycle, actual cycle duration is calculated as follows:
  - Actual Cycle Duration = last date of non-zero study treatment– cycle start date + 1.

The cycle day will be calculated as:

Cycle day = Date of the assessment/event – cycle start date + 1.

#### **Intensive Chemotherapy Study**

Study day in association with study period will be displayed for intensive chemotherapy patients, ie, Induction 1, Induction 2 (optional), Cytarabine Consolidation Cycle 1 through 4 (optional), HSCT period (optional), Post-consolidation Cycle 1, 2, 3, etc (optional). Note that a patient who undergoes consolidation therapy can either go on Cytarabine Consolidation and/or HSCT.

Cycle start and end dates are derived per patient and not per study treatment.

For all cycles other than the HSCT period.

- For any cycle, the actual cycle start date for each subject is the earliest start date of dosing (dose >0 at that visit ) in that cycle CRF exposure page.

- For all but the last cycle.
  - actual cycle end date is calculated as the start date of the next cycle minus one day.
  - actual cycle duration is calculated from Day 1 of a cycle to the day prior to Day 1 of the next cycle, as follows:

$$\text{Actual Cycle Duration} = \text{cycle end date} - \text{cycle start date} + 1.$$

- For the last cycle, actual cycle duration is calculated as follows:
  - Actual Cycle Duration = last date of non-zero study treatment – cycle start date + 1.

The cycle day will be calculated as:

$$\text{Cycle day} = \text{Date of the assessment/event} - \text{cycle start date} + 1.$$

#### HSCT Period

The HSCT period is defined as time from the start of the HSCT conditioning regimen until the subject re-starts glasdegib/placebo or cytarabine, death, post study follow-up, or withdrawal. Day 1 is the day of the HSCT. Note that in the Protocol this was referred to as Day 0 per common clinical practice. Per Protocol Section 8, there are limited data collection during the HSCT period beyond 28 days after the last investigational treatment administration prior to HSCT.

The cycle day for assessments occurring on or after the day of HSCT will be calculated as:

$$\text{Cycle day} = \text{Date of the assessment/event} - \text{date of HSCT} + 1.$$

The cycle day for HSCT conditioning regimen(s) will be negative as they occur prior to HSCT and calculated as:

$$\text{Cycle day} = \text{Date of the assessment/event} - \text{date of HSCT}.$$

#### **5.2.4. Date of Last Contact**

The date of last contact will be derived for patients not known to have died at the data cutoff date using the latest complete date (ie, imputed dates will not be used in the derivation) among the following:

- All patient assessment dates (eg, blood draws (laboratory, Pharmacokinetics (PK)), vital signs, physical exam, performance status, ECG, Echocardiograms (ECHO)/MUGA scans, disease assessments).
- Start and stop dates of concomitant therapies including non-drug treatments or procedures.

- Completion dates for PRO Questionnaires.
- Start and end dates of anti-cancer therapies administered after study treatment discontinuation including systemic therapy, radiation, and surgeries.
- AE start and end dates.
- Last date known to be alive on the ‘Survival Follow-up’ CRF.
- Study treatment start and end dates.
- Hospitalization admission and discharge dates.
- Randomization date, and
- Date of discontinuation on disposition CRF pages (do not use if reason for discontinuation is lost to follow-up or death).

Only dates associated with actual examinations of the patient will be used in the derivation. Dates associated with a technical operation unrelated to patient status such as the date a blood sample was processed or dates data were entered into the CRF will not be used. Assessment dates after the data cutoff date will not be applied to derive the last contact date.

#### **5.2.5. Disease Assessment Date**

Date of assessment from the hematologic response CRF will be used as the date of response. Date of hematologic relapse will be derived as the earliest date from the peripheral blood blasts, bone marrow blasts, or EMD assessment where the criteria for relapse is met. For hematologic relapse occurring during long-term follow-up, the date of assessment from the hematologic response CRF will be used.

#### **5.2.6. Unscheduled Assessments**

Unless otherwise specified, unscheduled assessments will not be displayed in summary tables by nominal visit/timepoint. Unscheduled assessments will be used when deriving baseline and worst case on-treatment for safety and PRO analyses (except where noted for baseline ECGs). Additionally, unscheduled disease assessments will be used for efficacy analyses (eg, defining date of relapse/censoring, CRi or better, date of last contact).

#### **5.2.7. Standard Derivations and Reporting Conventions**

The following conversion factors will be used to convert days into weeks, months or years: 1 week = 7 days, 1 month = 30.4375 days, 1 year = 365.25 days.

Percentages will be reported to one decimal place. The rounding will be performed to closest integer/first decimal using the common mid-point between the two consecutive values, eg, 5.1 to 5.4 will be rounded to an integer of 5, and 5.5 to 5.9 will be rounded to an integer of 6.

### 5.2.8. Analyses for Continuous Data

Continuous variables will be summarized using descriptive statistics ie, number of non-missing values and number of missing values [ie, n (missing)], mean, median, standard deviation (SD), minimum, maximum and first and third quartile (Q1 and Q3). CCI [REDACTED] PK summaries will also include coefficient of variation percent (%CV).

In case the analysis refers only to certain visits, estimates will be based on the number of patients with an assessment at that visit, unless otherwise specified.

### 5.2.9. Analyses for Categorical Data

Qualitative variables will be summarized by frequency counts and percentages. Unless otherwise specified, the calculation of proportions will include the missing category. Therefore counts of missing observations will be included in the denominator and presented as a separate category.

In case the analysis refers only to certain visits, percentages will be based on the number of patients with an assessment at that visit, unless otherwise specified.

### 5.2.10. Analyses for Time to Event Data

The stratified log-rank test will be used for comparing treatments. Hazard ratios and the associated 95% two-sided confidence intervals are estimated by Cox proportional hazards (PH) model. Repeated confidence interval will also be provided, to account for alpha spending, when appropriate.

Time to event endpoints will be summarized using the Kaplan-Meier method and estimated survival curves will be displayed graphically when appropriate. Graphs will describe the number of patients at risk over time. The median, first and third quartiles, and probabilities of an event at particular points in time will be estimated by the Kaplan-Meier method. Confidence intervals for medians and quartiles are based on the Brookmeyer-Crowley method. Confidence intervals for the estimated probability of an event at a particular timepoint will be generated using the log(-log) method with back transformation to a confidence interval on the untransformed scale. Summaries of the number and percentages of patients with an event and reason for censoring will also be provided on summary tables and/or figures.

If a cumulative incidence analysis is performed, the stratified Gray's test will be used for comparing treatments. Hazard ratios and the associated 95% two-sided confidence intervals are estimated by a proportional subdistribution hazards model. The 25th, 50th, and 75th percentiles and probabilities of an event at particular points in time will be estimated from the cumulative incidence curve. Confidence intervals for the estimated probability of an event at a particular timepoint will be generated using the delta method with a log(-log) transformation for the standard error.

## 5.3. Methods to Manage Missing Data

Unless otherwise specified, all data will be evaluated as observed, and no imputation method for missing values will be used.

Any imputations will occur at the analysis dataset level. Additionally, in all patient data listings imputed values will be presented and flagged as imputed.

Missing statistics, eg, when they cannot be calculated, should be presented as 'ND' for not done, 'NR' for not reached or 'NA' for not applicable. For example, if N=1, the measure of variability cannot be computed and should be presented as 'ND' or 'NA'.

CDISC Safety Rulebook will be followed when handling the missing/partial dates, treatment emergent AE algorithm, missing AE grades, etc.

### **5.3.1. Missing Dates**

For purposes of data listings, dates will reflect only the information provided by the investigator on the CRF.

If start dates for adverse events or concomitant medications are completely missing a worst case approach will be taken whereby the events will be considered treatment emergent and the medications will be considered concomitant. If only partial information are available (eg, only a month and year or only a year) and the partial information provide sufficient information to indicate the dates are prior to the start of study treatment (eg, month/year less than month/year of first dose) then these will be considered to have started prior to treatment; otherwise a similar worst case approach will apply and these will be considered to have started after treatment.

### **Date of Last Dose of Study Treatment**

No imputation will be done for first dose date. Date of last dose of study treatment, if unknown or partially unknown, will be imputed as follows:

- If the last date of study treatment is completely missing and there is no Disposition CRF page for the treatment phase and no death date, the patient should be considered to be ongoing and use the data cutoff date for the analysis as the last dosing date; or
- If the last date of study treatment is completely or partially missing and there is EITHER a Disposition CRF page for the treatment phase OR a death date available (on or prior to the data cutoff date), then impute this date as the last dose date:

= 31DECYYYY, if only Year is available and Year < Year of min (Date of Completion/Discontinuation from the Disposition CRF page for the treatment phase, death date),

= Last day of the month, if both Year and Month are available and Year = Year of min (Date of Completion/Discontinuation from the Disposition CRF page for the treatment phase, death date) and Month < the month of min (EOT date, death date), or

= min (Date of Completion/Discontinuation from the Disposition CRF page for the treatment phase, death date), for all other cases.

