## Date of Start of New Anti-cancer Therapy

Incomplete dates for new anti-cancer therapy will be imputed as follows and will be used to determine censoring dates for efficacy analyses. Note that HSCT before the end of the treatment phase or its conditioning regimen(s) are not considered new anti-cancer therapies.

- The end date of new anti-cancer therapy will be included in the imputation for start date of new anti-cancer therapy. If the end data of new anti-cancer therapy is:
  - completely missing then it will be ignored in the imputations below,
  - partially missing with only year available then the imputations below will consider 31DECYYYY as the end date of the new anti-cancer therapy, or
  - partially missing with only month and year available then the imputations below will consider the last day of the month for MMMYYYY as the end date of the new anti-cancer therapy.
- For patients who have not discontinued study treatment at the time of the data cutoff date, last dose of study treatment is set to the data cutoff date in the imputations below.
- If the start date of new anti-cancer therapy is completely or partially missing then the imputed start date of new anti-cancer therapy is:

= 31DECYYYY, if only Year is available and Year < Year of min  
[max (PD/relapse date + 1, last dose of study treatment + 1), end date of new  
anti-cancer therapy]

= Last day of the month, if both Year and Month are available and

Year = Year of min [max (PD/relapse date + 1, last dose of study  
treatment + 1), end date of new anti-cancer therapy]

Month < Month of min [max (PD/relapse date + 1 day, last dose of study treatment + 1 day), end date of new anti-cancer therapy]

= min [max (PD/relapse date + 1, last dose of study treatment + 1), end date of new anti-cancer therapy], for all other cases.

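### SAP 5.3.1: a partial date with a known month in an earlier calendar year is imputed past that month, usually by days for last dose and occasionally by months

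*SAP*

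**What the plan says.** SAP 5.3.1 (Date of Last Dose of Study Treatment) applies three branches to a partial date when a treatment-phase disposition page or a death date exists. Call the earlier of those two dates the reference date R.

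1. Year only, before the year of R: "31DECYYYY, if only Year is available and Year < Year of min" of R, giving 31 December.
2. Year and month known: "Last day of the month, if both Year and Month are available and Year = Year of min" of R, together with "Month < the month of min (EOT date, death date), or", giving the last day of the recorded month.
3. Everything else: "min (Date of Completion/Discontinuation from the Disposition CRF page for the treatment phase, death date), for all other cases", that is, R itself.

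SAP 5.3.1 (Date of Start of New Anti-cancer Therapy) has the same structure. Its second branch requires "Year = Year of min [max (PD/relapse date + 1, last dose of study" and "Month < Month of min [max (PD/relapse date + 1 day, last dose of study treatment + 1 day), end date of new anti-cancer therapy". Its residual branch is "min [max (PD/relapse date + 1, last dose of study treatment + 1), end date of new anti-cancer therapy], for all other cases".

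These dates are used in several places:
- Safety on-treatment window, 28 days after last dose and closed earlier by new therapy (SAP 3.5).
- Glasdegib treatment duration and dose intensity (SAP 6.5.3.1).
- Deaths within 28 days of last dose (SAP 6.6.2).
- The cut-off of secondary efficacy data at new therapy (SAP 3.2.1). SAP 5.3.1 itself says the imputed new-therapy date determines efficacy censoring.

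**The concern.** The end-of-month branch tests for equality of years, and the year-only branch requires the month to be unknown. A record such as November 2019 with a reference date in early 2020 satisfies neither. It drops to the residual branch, and the month and year on the CRF are discarded.

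This gives a wrong date; it is not merely an unstated detail. Within one calendar year the same pattern is handled sensibly, and a record holding only the year 2019 is placed at 31 December 2019. So a site that supplies more information gets a later and less accurate date. The SAP's own rule for other partial stop dates (5.3.1, Other Missing or Partial Dates) uses the last day of the recorded month with no year condition.

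At stake are the classification of adverse events and deaths near the end of treatment, glasdegib exposure, and which relapses count in the secondary efficacy endpoints. Last dose is also an input to the new-therapy rule, so one error can feed the other.

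**Working it through.** The plan gives no figure to reproduce; the check is of branch logic. I assume that the EOT date in the month condition is the same disposition date named elsewhere in the rule. All calendar dates below are illustrative.

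**Reference dates**
- Last dose: R = min(disposition date, death date).
- New therapy: R = min[max(relapse + 1, last dose + 1), end of new therapy]. A wholly missing end date is ignored.

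**Rule as printed against the rule with branch 2 tested on year and month together**

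| Item | Recorded | R | As printed | Corrected | Difference |
|---|---|---|---|---|---|
| Last dose | Sep 2019 | 20 Nov 2019 | 30 Sep 2019 | 30 Sep 2019 | 0 |
| Last dose | 2019 only | 20 Jan 2020 | 31 Dec 2019 | 31 Dec 2019 | 0 |
| Last dose | Dec 2019 | 1 Jan 2020 | 1 Jan 2020 | 31 Dec 2019 | 1 day |
| Last dose | Dec 2019 | 14 Jan 2020 | 14 Jan 2020 | 31 Dec 2019 | 14 days |
| Last dose | Nov 2019 | 20 Jan 2020 | 20 Jan 2020 | 30 Nov 2019 | 31 + 20 = 51 days |
| New therapy | Sep 2019 | 16 Dec 2019 | 30 Sep 2019 | 30 Sep 2019 | 0 |
| New therapy | Nov 2019 | 16 Feb 2020 | 16 Feb 2020 | 30 Nov 2019 | 31 + 31 + 16 = 78 days |

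In the last row, last dose is 10 Oct 2019, relapse is 15 Feb 2020 and the therapy end date is missing, so R = max(16 Feb 2020, 11 Oct 2019) = 16 Feb 2020.

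In every affected case the true date is no later than the end of the recorded month, and that month end is before R. If the recorded month is right, the corrected date is therefore always nearer the truth.

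**Size for last dose.** Let g be the days from true last dose to R. Overshoot = R minus the last day of the recorded month. With day-missing dates spread evenly over a 365-day year (an assumption), the share of those dates affected is g/365.

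| g | Share affected | Overshoot, min / mean / max (days) |
|---|---|---|
| 14 | 14/365 = 3.8% | 1 / 7.5 / 14 |
| 28 | 28/365 = 7.7% | 1 / 14.5 / 28 |
| 58 | 58/365 = 15.9% | 28 / 43.9 / 58 |
| 88 | 88/365 = 24.1% | 58 / 73.8 / 88 |

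For g = 14, last doses on 18-31 December give R on 1-14 January, hence 1 to 14 days past 31 December.

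The choices of g come from the protocol. The end-of-treatment visit is normally within 14 days of last dose (Table 1 footnote 29; Table 3 footnote 27). Section 5.5.5.1 sets a 28-day limit on interruptions the protocol does not require. The transplant interruption is at least 28 days before plus 30-60 days after, so 28 + 30 = 58 to 28 + 60 = 88 days.

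**Consequences in the examples**
- On-treatment window, November case: 20 Jan 2020 + 28 = 17 Feb 2020 as printed, against 30 Nov 2019 + 28 = 28 Dec 2019. It is 51 days longer unless new therapy closes it first.
- Deaths: if R is the death date, the printed rule puts last dose on the day of death, so the death counts as within 28 days. With R = 20 Jan 2020 the corrected interval is 51 days, which does not.
- New therapy: as printed, the relapse of 15 Feb 2020 precedes the imputed start of 16 Feb 2020 and counts. With 30 Nov 2019 it follows new therapy and is excluded.

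**The case against.** The strongest case against is about size and reach, since the branch logic reads as described.

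- **Size.** A reader might infer that last-dose dates typically move by weeks or months. The documents do not support that. If disposition is dated at the usual end-of-treatment visit, the overshoot is at most 14 days. A gap of about 80 days would need transplant without resumption, a non-toxicity interruption handled with the sponsor (Protocol 5.5.5.2), or a late disposition date. This stands.
- **Dose intensity.** A reader might infer that relative dose intensity is affected for every drug. It is not. Induction cytarabine and daunorubicin divide by days with a non-zero dose, azacitidine divides by seven days times the number of dosed cycles, and consolidation cytarabine has no relative dose intensity (SAP 6.5.3.2 to 6.5.3.5). Only glasdegib uses treatment duration. Even there, SAP 6.5.3.1 counts interruptions up to permanent discontinuation and removes the transplant period, so part of the added interval might be counted, or excluded, in any case. The effect on glasdegib duration itself is direct.
- **Adverse events.** Active collection need only run 28 days after last administration (Protocol 8.1.4), and recording of non-serious events ends at new anticancer therapy (8.1.4.2). Misclassification is possible where collection ran longer, but not automatic.
- **Efficacy.** A reader might infer a threat to the primary analysis. There is none. OS is not censored at new therapy (SAP 3.1), and the last-contact date excludes imputed dates (SAP 5.2.4). For an extra relapse to count in a secondary endpoint, therapy must start before relapse with its day missing, R must fall in a later year, and the therapy end date must not pull R back.
- **Frequency.** Dosing diaries and preparation records (Protocol 5.3) should make missing dosing days uncommon. No count is given.
- **Rulebook.** SAP 5.3 says a CDISC Safety Rulebook governs partial dates. Its content is not in the documents, so one cannot assert that every affected record will be wrong. Equally, it is not shown to cure the gap. If it differs, the SAP holds two conflicting rules and still needs the edit.

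**Conclusion.** The point holds as a minor drafting error in two explicit rules. Read literally, both send a known month and year from an earlier calendar year to the reference date, outside the month the site recorded.

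For last dose the usual overshoot is 1-14 days, on the assumption that disposition is dated within the normal end-of-treatment window. Weeks to months occur only when the reference date is much later. Affected quantities are the on-treatment window, glasdegib duration and possibly its dose intensity, deaths within 28 days of last dose, and the new-therapy cut for secondary efficacy endpoints. Primary OS is untouched.

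The conclusion assumes the rules are programmed as printed. The number of affected records cannot be derived from the documents and is probably small, so this is worth correcting but does not endanger the trial's main conclusion.

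**What to change.** In both rules, restate the end-of-month branch so that it applies when month and year are available and either Year < reference year, or Year = reference year and Month < reference month. The imputed date is then the last day of the recorded month. Leave the year-only and residual branches unchanged; the year-only and same-year cases tested above give the same dates under either wording.

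The cost is one clause in each of two SAP rules and a one-line program edit, best made before unblinding. At the same time, confirm that the Rulebook cited in SAP 5.3 gives the same result.
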